NCT NCT05319795

STUDY PROTOCOL

Exploring the Efficacy of the Effortful Swallow Maneuver for Improving Swallowing in People with Parkinson Disease

PI: [name]. ¹

Co-I: [name], Ph.D. ²

¹ Toronto Rehabilitation Institute – University Health Network

² Edmond J Safra Program in Parkinson's Disease and Morton and Gloria Shulman Movement Disorders Clinic, Toronto Western Hospital, University of Toronto

Contents

LIST OF ABBREVIATIONS	3
Background Information	4
Study Objectives and Hypotheses	4
Outcome measures:	4
Hypotheses	5
Study Design.....	5
Selection of participants:	5
Inclusion Criteria.....	5
Review of consent form:	6
Baseline study appointment procedures:	6
Study Intervention	9
Risks	10
Benefits	11
Honorarium	11
Data processing and analysis	11
Statistics.....	11
Conflicts of interest	11
Direct Access, Handling and Record Keeping of Source Data	12
Quality Control and Quality Assurance Procedures.....	12
References.....	12

LIST OF ABBREVIATIONS

ASPEKT	Analysis of Swallowing Physiology: Events, Kinematics and Timing
ES	Effortful swallow
H&Y	Hoehn & Yahr
IOPI	Iowa Oral Performance Instrument
LVC	Laryngeal Vestibule Closure
mSv	Millisieverts
NIH	National Institutes of Health
PD	Parkinson Disease
PhAMPC	Pharyngeal area at maximum constriction
RES	Regular effort swallow
SRRL	Swallowing Rehabilitation Research Laboratory
TWH	Toronto Western Hospital
UHN	University Health Network
VFSS	Videofluoroscopic Swallowing Study

Background Information

Parkinson Disease (PD) is a common neurological disorder that is expected to affect 9 million people by 2030. Dysphagia (swallowing impairment) is highly prevalent in PD and can result in aspiration pneumonia, malnutrition, and dehydration. The most common intervention for dysphagia is the use of thickened liquids and modified food textures.

However, due to dissatisfaction with their texture and taste, sensation of increased satiety and increased thirst with increasingly viscous fluids, this approach is reported by patients to negatively impact swallowing-related quality of life.

The purpose of this study is to determine if an exercise-based approach called the Effortful Swallow maneuver is an effective intervention for dysphagia in PD that will enable people with PD and dysphagia to continue to consume regular foods and liquids.

Research has found that while there are no optimal interventions, exercise-based interventions targeting improved swallowing efficiency and muscle strength hold promise (El Sharkawi et al., 2002; Miles et al., 2017; Pitts et al., 2009; Athukorala et al., 2014; Troche et al., 2008). To select targeted exercise goals for dysphagia therapy, it is important to identify the physiological mechanisms contributing to swallowing impairment in PD. Studies identify two key mechanisms of swallowing impairment in PD: 1) prolonged time-to-laryngeal-vestibule-closure (time-to-LVC) which is a risk for aspiration; and 2) reduced pharyngeal constriction, leading to pharyngeal residue after the swallow (Ellerston et al., 2016; Nascimento et al., 2020; Curtis et al., 2020; Gandhi et al., 2021). In other patients with dysphagia, the Effortful Swallow (ES) maneuver is commonly used to target faster airway protection and improved bolus clearance (Hind et al., 2001; Fukuoka et al., 2013).

Study Objectives and Hypotheses

The objective of this project is to determine the immediate (compensatory effect) and long term efficacy (rehabilitative effect) of a 4-week program of the effortful swallow maneuver intervention on physiological swallowing parameters in Parkinson Disease. The Videofluoroscopic Swallowing Study (VFSS) recordings will be analyzed in duplicate according to a rigorous standard procedure known as the ASPEKT Method (Analysis of Swallowing Physiology: Events, Kinematics and Timing), from which the following outcomes will be measured. .

Outcome measures:

Primary Outcomes:

- Time-to-laryngeal vestibule-closure (i.e., the time interval between onset of the hyoid burst movement at the beginning of a swallow and achieving airway protection via closure of the laryngeal vestibule)
- Swallowing safety and airway protection status as measured by the Penetration-Aspiration Scale (Rosenbek et al., 1996)
- The degree of pharyngeal constriction during swallowing ("pharyngeal area at maximum constriction")
- The amount of residue left behind in the pharynx after a swallow.

Secondary Outcomes:

- The number of swallows per bolus
- Maximum value across 3 repetitions of a maximum tongue-palate press using the Iowa Oral Performance Instrument in an anterior position.

Hypotheses

We expect that use and repeated practice of the ES will lead to show differences post-intervention in swallowing function and physiology compared to baseline, as listed in the following table:

Parameter	Prediction post-intervention of effortful swallow maneuver (vs baseline regular effort swallows)
Primary outcomes:	
Time-to-Laryngeal-Vestibule-Closure (time-to-LVC)	Earlier closure leading to shorter time to laryngeal vestibule closure
Penetration-Aspiration Score (PAS)	Lower frequency of airway invasion events due to earlier time-to-LVC
Pharyngeal Area at Maximum Constriction (PhAMPC)	Smaller pharyngeal area at maximum constriction (i.e. better constriction)
Residue	Reduced pharyngeal residue due to better constriction
Secondary outcomes:	
# of swallows per bolus	Lower number of swallows per bolus due to better bolus clearance
Maximum anterior isometric pressure	Increased tongue pressure

Study Design

Participants with Parkinson Disease will be recruited over 18-24 months to participate in a dysphagia intervention protocol. This protocol will be a single arm feasibility study to determine the impact of the ES maneuver intervention on swallowing physiology. Participants who display prolonged time-to-LVC, and/or poor pharyngeal constriction during their baseline videofluoroscopic x-ray of swallowing (VFSS) compared to healthy reference values will be enrolled in a 4-week intervention program, with two 30-minute sessions of ES practice daily, 5 days per week. See Figure 1 for a summary of participant recruitment and study procedures.

Selection of participants:

Potential participants will be identified by staff at the Toronto Western Hospital's Movement Disorders Clinic, who will make contact to introduce the research program and obtain verbal consent to provide the study team with the participant's contact information (phone number and/or email, as preferred by the participant). The Movement Disorders Clinic staff will select potential participants based on the following criteria:

Inclusion Criteria

- At least 18 years old
- English-speaking

- Able to follow study instructions
- Neurologist confirmed diagnosis of PD
- Hoehn and Yahr scale score of 2 or 3
- Self-report of one or more swallowing or related symptoms:
 - ➔ Difficulty with secretion management
 - ➔ Coughing at the meal time
 - ➔ Choking on food
 - ➔ Respiratory infection in the past 6 months (other than COVID)

Exclusion Criteria

- History of head and neck cancer
- Radical neck dissection (e.g. anterior cervical spine surgery) or neck/ oropharyngeal surgery (not excluded – tonsillectomy, adenoidectomy)
- Past medical history of any neurological disease other than PD (e.g. multiple sclerosis, amyotrophic lateral sclerosis, traumatic brain injury, stroke)
- Cognitive or receptive communication difficulties that preclude the participant's ability to follow study instructions provided in English. This will be determined by the participant's physician prior to referring them to the study.

The target sample size is 12 participants. We expect the ratio of males: females to be 1.5:1, reflecting the ratio of males to females in the PD population.

Review of consent form:

All participants that express interest in participating and have agreed to allow the Movement Disorders clinic to share their contact information with the study team will be contacted by study personnel of the Swallowing Rehabilitation Research Laboratory. Participants that show continued interest after a brief introduction will be provided with the study information and consent form ahead of a telephone or video-conference call (using MS Teams) to answer any questions. We will proceed to schedule a study appointment after the participant confirms they have understood all the information that is provided and after verifying they have no more questions and wish to proceed. The formal written consent will be obtained at the beginning of the baseline study appointment, and a copy of the consent form will be provided to the participant. If a participant does not wish to participate in the study, they will no longer be contacted by study personnel; a decision not to participate will have no impact on clinical services provided.

Baseline study appointment procedures:

1) *Demographic and medical history information:*

Participants will be asked to complete a form capturing demographic, medical history and history of PD symptoms. The following data will be collected:

- i. Year of birth
- ii. Sex
- iii. Relevant medical history and ongoing treatments (e.g. presence/location of a deep brain stimulator).
- iv. Race/ethnicity
- v. Time post-onset of symptoms (initial and swallowing-specific);
- vi. Allergies to barium contrast, food thickeners or latex.

- b. Participants will be requested to complete a 26 item validated questionnaire entitled the *Munich Dysphagia Test – Parkinson’s Disease* to understand the nature of swallowing difficulties experienced and associated burden.

2) **Tongue strength:**
 Bulbar muscle strength will be measured using 3 repetitions of a maximum effort isometric tongue-to-palate press task using the Iowa Oral Performance Instrument (IOPI). A clean, single-use disposable tongue bulb will be used for each participant.

3) **VFSS:**
Stimulus preparation: Bracco E-Z-Paque® powdered barium will be prepared in 20% w/v concentration with water, and thickened to target consistency using Resource Thicken-Up™ Clear (a xanthan gum thickener developed by Nestlé Health Science). Target consistency will be defined using the International Dysphagia Diet Standardisation Initiative definitions and Flow Test. All stimuli will be prepared no longer than 6 hours prior to scheduled use, according to a strict standard operating procedure.

Procedure: Three cups of each stimulus will be prepared for the experiment, each containing 40 ml and organized in a muffin tray placed in front of the participant (please see table below for the order of the exams). The participant will be asked to take a comfortable sip from each cup. The cups will be weighed on a digital balance at the conclusion of the session to derive estimates of sip volume.

Recording: The videofluoroscopic swallowing study will be captured in lateral projection using pulsed videofluoroscopy at a rate of 30 pulses per second, and recorded on a synchronized videocapture system at 30 frames per second.

[figure not shown]
Timeline and location: A baseline VFSS will be conducted by speech-language pathologists at the Outpatient Swallowing Clinic at Toronto Western Hospital’s Gastric Suite.

Order of stimuli:

- i. Saliva swallow (with no external barium bolus) to be used for land-marking
- ii. Up to 3 regular effort swallows of thin liquid
- iii. Up to 3 effortful swallows of thin liquid
- iv. Up to 3 regular effort swallows of mildly-thick liquid
- v. Up to 3 effortful swallows of mildly-thick liquid

Intervention eligibility: Participants that display prolonged time-to-LVC measures and/or poor pharyngeal constriction measures compared to healthy reference values on the baseline VFSS with thin or mildly thick stimuli will be eligible for the intervention portion of this research study (described below). Once a participant has been deemed eligible, staff at the Toronto Western Hospital’s Movement Disorders Clinic will then provide the study personnel with an updated Hoehn & Yahr scale score and medication list prior to proceeding with the intervention. Participants who do not display impaired time-to-LVC and/or PhAMPC on the baseline VFSS will be withdrawn and will not continue to the intervention portion of the study.

Figure 1. Summary of participant recruitment and study procedures

Study Intervention

A 4-week intervention program with two 30-minute sessions of ES practice daily, 5 days per week will be offered to eligible participants based on confirmation of intervention candidacy in the baseline VFSS.

Practice will be supervised on a reducing schedule (week 1: 5 sessions; week 2: 4 sessions, etc.), via a secure videoconference using Microsoft Teams. Which days the intervention will be performed and supervised will be dependent on the availability of the participant and the study team member. This will be determined at the start of the protocol with each participant. There is no requirement to practice at the same time each day or to practice on the same days of the week each consecutive week.

Intervention will involve biofeedback provided using the Iowa Oral Performance Instrument. An IOPI device will be loaned to each participant for home use at the end of baseline videofluoroscopy, and a set of disposable pressure bulbs will be provided to cover the course of intervention. Participants will not be held responsible for lost or broken devices. Additionally, a supply of thickener will be provided to each participant for use in home practice sessions. Instruction in use of all supplies will be provided.

Practice Sessions: Each session will include:

- 15 regular saliva swallows with the IOPI bulb in place. The mark on the connecting tube will be aligned with the upper incisors. A rest period of 20 seconds will be utilized between saliva swallow.
- 15 effortful saliva swallows with the IOPI bulb in place. The mark on the connecting tube will be aligned with the upper incisors. A rest period of 20 seconds will be utilized between saliva swallow.

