- c) All x-rays, including the video x-ray in this study, involve low levels of radiation exposure. Radiation exposure always carries a risk of radiation effects (such as cancer). We manage these risks by following standard procedures and keeping radiation dose as low as possible. The following information should help to explain this risk:
 - a. The risk of developing cancer changes based on sex and age. Lifetime cancer risks associated with a full clinical video swallowing x-ray are:
 - i. for 60-year-old male: 4.9 per million
 - ii. for a 60-year-old female: 7.2 per million
- d) The x-ray is expected to show whether or not the participant has swallowing impairment. We are looking for two specific types of swallowing problem:
 - a. Food or liquid going into their airway ("aspiration").
 - b. Food or liquid getting stuck in their throat (which we call "residue").
 If either of these problems occur during the study, the SLP will follow standard procedures to encourage the participant to expel the material and decide when study VFSS trials and/or exams need to be terminated early.

Incidental Findings

A swallowing x-ray captures information regarding the structures of the neck and how they move during swallowing. It is possible that the VFSS may contain evidence of other, unexpected findings that are noticed by the study speech-language pathologist (such as a diverticulum or a mass). In such cases, the study licensed speech-language pathologist will follow routine clinical

[name]. *Effortful Swallow maneuver for Swallowing Impairment in Parkinson Disease*

Version date: Jan 14, 2022

CAPCR-ID: 21-5814

procedures and ask the on-call radiologist to review the VFSS. If appropriate, the radiologist will generate a clinical report documenting the observation. The consent form includes a check box prior to the signature line, asking the participant to indicate whether or not they wish to be told about incidental findings

Benefits

There may or may not be benefits to taking part in the study. Benefits from participating in the study include potential amelioration of swallowing difficulties, and furthering knowledge regarding interventions for swallowing impairment in the Parkinson Disease population.

Honorarium

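### Effortful swallows always follow regular swallows of the same consistency, with no stated handling of residue already present, so carry-over can confound the immediate residue contrast

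*Combined protocol and SAP*

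**What the plan says.** Under Outcome measures, residue is the fourth primary outcome: "The amount of residue left behind in the pharynx after a swallow". The line mentions no pre-swallow value.

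The baseline Order of stimuli is a fixed list. After a saliva swallow used for landmarking come "Up to 3 regular effort swallows of thin liquid", then "Up to 3 effortful swallows of thin liquid", then "Up to 3 regular effort swallows of mildly-thick liquid", then "Up to 3 effortful swallows of mildly-thick liquid". After the intervention (Post-intervention VFSS appointment) only the two regular blocks are taken, thin then mildly thick.

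Study Objectives names an immediate, compensatory effect alongside the long-term one. Statistics plans Wilcoxon signed rank tests among baseline RES, baseline ES and post-intervention RES, with bolus clearance among the measures. It has no term for order or prior residue. Data processing randomises the clips for rating, not the order in which boluses are swallowed.

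The one provision for clearing residue is in Risks, item d): when aspiration or residue occurs, "the SLP will follow standard procedures to encourage the participant to expel the material".

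**The concern.** A reading of what is in the pharynx after a swallow can include what earlier boluses left there. Within each consistency the regular sips come first, so the effortful sips may start from a dirtier pharynx. No participant has the opposite order to balance this. Randomising clips protects the raters from bias but does not change what was in the pharynx when each clip was recorded.

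The population makes this more than theoretical. The background names reduced constriction leading to residue as a key mechanism in Parkinson disease, and entry to the intervention requires prolonged time-to-LVC and/or poor constriction. With a target of 12 participants, a null or small immediate residue effect could not be told apart from inherited barium.

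**Working it through.** **Inputs from the documents.** There are up to three sips per block. At baseline this gives positions 1–3 RES thin, 4–6 ES thin, 7–9 RES mildly thick and 10–12 ES mildly thick. The plan gives no residue rate, persistence share or effect size, so there is no figure of its own to reproduce.

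**Assumptions, for illustration.** Bolus k leaves a deposit d_k, and a share c of standing residue persists to the next reading. All three sips are taken, and ES has no true effect. Then R_k = d_k + c·R_(k−1), with R_0 = 0.

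**Example, c = 0.3, all deposits 1.** R_1 to R_6 are 1, 1.3, 1.39, 1.417, 1.4251 and 1.4275. The mean of positions 1–3 is 3.69/3 = 1.230. The mean of positions 4–6 is 4.2696/3 = 1.4232. The ratio is 1.157.

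| c | thin RES mean | thin ES mean | thin ES excess | mildly thick ES excess, equal deposits | mildly thick ES excess, deposit 1.5 |
|---|---|---|---|---|---|
| 0.1 | 1.0700 | 1.1111 | 3.8% | 0.00% | 1.2% |
| 0.3 | 1.2300 | 1.4232 | 15.7% | 0.01% | 4.7% |
| 0.5 | 1.4167 | 1.9271 | 36.0% | 0.4% | 9.8% |

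The mildly thick excess is small with equal deposits because regular mildly thick sips already inherit residue from the effortful thin block.

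**Clearing between sips.** Write c = r(1 − q), where r is the share left per swallow and q the share of old residue cleared between sips. For r from 0.05 to 0.30 the thin excess is 1.8% to 15.7% at q = 0, 0.9% to 6.2% at q = 0.5, 0.2% to 1.0% at q = 0.9, and zero at q = 1.

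**If ES truly reduces residue by 30%** (equal deposits; c = 0.1, 0.3, 0.5):
- ES acts only on the new bolus: mildly thick reads −28%, −23% and −15%.
- ES acts on everything in the pharynx, R_k = 0.7(1 + c·R_(k−1)): thin reads −29%, −24% and −16%; mildly thick reads −30% to −31%.

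The sign of the mildly thick bias therefore depends on how the manoeuvre acts.

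**Pre/post contrast.** Regular thin comes first at both visits. Regular mildly thick follows six thin sips at baseline, the last three effortful, but three regular thin sips post-intervention. With no effect of any kind and c = 0.5, the post mean is 1.9271 (positions 4–6) and the baseline mean is (1.9844 + 1.9922 + 1.9961)/3 = 1.9909, a difference of −3.2%. If ES clears 30% of everything at baseline and there is no training effect, the post value reads 0.6% to 5.1% higher (r = 0.05 to 0.30, q = 0). The direction is again not fixed.

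**Why not subtract.** At c = 0.3 with no ES effect, the mean after-minus-before change is 1.39/3 = 0.463 for RES thin and (1.4275 − 1.39)/3 = 0.0125 for ES thin. Subtraction would credit ES with almost complete clearance that did not happen.

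**Adjacent swallows, thin.** R_4/R_3 is 1.111/1.110, 1.417/1.390 and 1.875/1.750, an excess of 0.1%, 1.9% and 7.1%.

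**The case against.** The strongest reply is that the documents do not show how residue is actually scored. Ratings follow the ASPEKT method and standard operating procedures that are not reproduced. These may already deal with pre-existing residue, or specify which swallow of a bolus is scored. In addition, expulsion is prompted when residue occurs, and extra swallows per bolus are expected and counted; both push persistence down. The tabulated hypotheses compare post-intervention with baseline regular swallows, so the immediate contrast is not the one they address, and the study is a 12-person single-arm feasibility study.

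Much of this stands as a limit on size. It does not remove the point. The expulsion prompt has no stated threshold and no check that the pharynx is clear before the next sip. Nothing visible says that ASPEKT nets out prior residue; if it does, one sentence in the protocol settles the matter. The immediate effect is a stated objective with a planned test, and the pre/post contrast for mildly thick is touched too.

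Counterbalancing the blocks is the obvious design alternative. It would balance carry-over across participants on average but would not remove it from individual readings.

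**Conclusion.** The concern holds as a risk of confounding. Fixed order, an outcome read after the swallow and no stated handling of prior residue leave the immediate residue contrast mixed with carry-over. The likely direction is against ES for thin liquid. For mildly thick it is near zero or uncertain.

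The percentages rest on an assumed persistence of 0.1 to 0.5, three sips per block and no true effect. They show a range and do not estimate what this trial will see.

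A reader might infer that the contrast is certainly biased against the manoeuvre in both consistencies, or that a 36% benefit would be cancelled. The documents support neither. The mildly thick comparison is almost unbiased under the same model with equal deposits. The 36% needs the highest persistence considered and a manoeuvre that clears none of the standing residue; if ES acts on everything present, the cancelling reductions for thin are about 3.5%, 11% and 20%. Whether barium is in fact left between sips is also not documented.

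**What to change.** 1. State in Data processing and analysis how residue present before a bolus is treated, and which swallow of a bolus is scored. If ASPEKT already covers this, say so.
2. Otherwise, on the existing clips, rate residue on the last recorded frame before each bolus, where one exists, as well as after the swallow. Report how many clips lack such a frame, since the correction cannot be made for those.
3. In the residue contrasts, both RES v ES and pre v post, analyse post-swallow residue adjusted for the pre-bolus value. One way is a per-swallow model with a participant effect, condition, consistency and pre-bolus residue. Do not use the simple difference.
4. Add a sensitivity comparison of the last regular with the first effortful swallow of the same consistency. Note that it reduces carry-over bias but does not remove it, and that it uses one swallow per condition.

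Cost: baseline has up to 4 × 3 = 12 boluses and post-intervention up to 2 × 3 = 6, so 18 per participant and 12 × 18 = 216 extra tracings at most. There is no new imaging; the downside is rating time.

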Once participants have completed all study steps, they will be given \$100 in the form of an e-gift card for their time and effort. Participants that drop out early but have completed at least 2 weeks of the intervention protocol, will be given \$50 in the form of an e-gift card. Compensation will be provided upon return of loaned study equipment.

Data processing and analysis

All data processing and analysis will take place at SRRL – TRI. Prior to data analysis, each VFSS will be de-identified by study staff at TRI and the audio signal will be removed to limit the communication of any information that might bias the raters. The de-identified recordings will then be segmented into bolus clips which will be randomized for rating. Blinded rating will be completed by trained raters (minimum of 30% to be completed in duplicate to ensure reliability). Raters will additionally be blinded to VFSS time-point (pre vs post-intervention), time post Parkinson Disease diagnosis and bolus consistency. The bolus clips will be analyzed by the Swallowing Rehabilitation Research Lab using the ASPEKT method.

Statistics

We will use Wilcoxon signed rank tests to show differences between baseline regular effort swallow (RES), baseline ES and post-intervention RES in the frequency and severity of impairment in time-to-LVC, pharyngeal constriction, airway protection and bolus clearance.

Conflicts of interest

[name], the principal investigator, holds current and prior research contracts with Bracco Canada and Nestlé Health Science, who are manufacturers of the barium products and thickening agents that will be used in this study. She has also served in an advisory capacity on expert panels for Nestlé Health Science. All products for use in the study will be purchased. Neither Bracco Canada nor Nestlé Health Science will have any role as sponsors of this study. [name] will not receive any financial payment, either personally or to the lab, related to the use of Nestlé or Bracco products in this study. Additionally, we will be preparing liquids of different thicknesses (thin and mildly thick) in this study. The definitions of these thicknesses come from a recent framework developed by the International Dysphagia Diet Standardisation Initiative (www.iddsi.org). [name] is a member of the board of directors for IDDSI.

Participants will be made aware of these relationships during the consent discussion.

Direct Access, Handling and Record Keeping of Source Data

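### The baseline VFSS that decides entry on time-to-LVC and/or PhAMPC is also the baseline for those two primary outcomes, so in a single arm their pre-post change cannot be separated from regression to the mean

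*Combined protocol and SAP*

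**What the plan says.** The protocol contains the statistical plan; there is no separate SAP.

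- **Objective** (Study Objectives and Hypotheses): to "determine the immediate (compensatory effect) and long term efficacy (rehabilitative effect) of a 4-week program". Time-to-LVC and PhAMPC are two of the four primary outcomes. The other two are the Penetration-Aspiration Scale (PAS) and residue.
- **Prediction** (Hypotheses): the table column reads "Prediction post-intervention of effortful swallow maneuver (vs baseline regular effort swallows", and a fall is predicted for both measures.
- **Design** (Study Design): "This protocol will be a single arm feasibility study to determine the impact of the ES maneuver intervention on swallowing physiology". Selection of participants adds: "The target sample size is 12 participants".
- **Entry** (Intervention eligibility): a participant is treated on the strength of "prolonged time-to-LVC measures and/or poor pharyngeal constriction measures compared to healthy reference values on the baseline VFSS", with either consistency able to qualify. Of the rest: "Participants who do not display impaired time-to-LVC and/or PhAMPC on the baseline VFSS will be withdrawn".
- **Exams**: the baseline VFSS has up to 3 RES and up to 3 effortful swallows (ES) at each of two consistencies. There is one post-intervention VFSS, at the end of the 4 weeks, with RES only.
- **Analysis** (Statistics): Wilcoxon signed rank tests between baseline RES, "baseline ES and post-intervention RES in the frequency and severity of impairment in time-to-LVC, pharyngeal constriction", airway protection and bolus clearance. No adjustment for selection is described.
- **Rating** (Data processing and analysis): every VFSS is cut into clips, randomized and rated blind to time-point. Quality Control plans inter-rater reliability only.

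**The concern.** A person's reading on one day is their usual level plus day-to-day and swallow-to-swallow variation. People chosen because the reading was high will, on average, have had unfavourable variation that day. A second exam draws fresh variation, so the group average falls even if nothing has changed. The Hypotheses table predicts a fall in the same direction.

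The plan has no control arm, second baseline or untreated follow-up against which to judge the fall. As worded, it would let a fall in time-to-LVC or PhAMPC be reported as long-term rehabilitative efficacy, which this design cannot show for the two measures that decide entry.

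**Working it through.** **Plan's own figure.** The target of 12 comes without alpha, power, effect size or SD, so there is nothing to reproduce. The documents also give no cut-offs, reliabilities or share eligible. Every size below rests on assumptions.

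**Step 1: mechanism.** Write baseline = person + day 1 + bolus 1, and re-test = person + day 2 + bolus 2, with no treatment effect. Selection on high baseline values makes the expected day 1 and bolus 1 terms positive, while those at re-test average zero. For one normal measure with exam-to-exam reliability r and a cut-off c SD above the mean of those screened:

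expected fall = (1 − r) × φ(c) / (1 − Φ(c))

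With r = 0.7 and c = 0.5: 0.3 × 0.352 / 0.309 = 0.3 × 1.141 = 0.34 participant-level SD.

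The plan's either-measure rule dilutes this, because some people enter on the other measure. Simulation with true-score correlation 0.3 gives 0.14 SD at the same setting. The two-sided test is then significant in 7.6% of trials, against 4.2% without selection. Over r = 0.5 to 0.9 and c = 0 to 1, the fall is 0.03 to 0.35 SD and the rate 4.6 to 16.6%.

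**Step 2: a model closer to the exam.** Assumptions:

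- normal values; single-bolus variance 1, equal in patients and healthy people;
- person share of variance 0.3, 0.5 or 0.7; day share 0, 0.1 or 0.2;
- cut-off 1 or 1.5 SD above the healthy mean;
- two independent measures, two consistencies, 3 RES boluses each; any of the four consistency means above the cut-off qualifies;
- analysed value is the mean of 6 RES boluses;
- 12 treated, no true effect, two-sided alpha 0.05.

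For n = 12 the rank sum is at most 12 × 13 / 2 = 78. The exact test declares improvement at W+ ≥ 65, with probability 0.0212. For at least one of the two measures the nominal rate is 1 − (1 − 0.0212)² = 4.2%.

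| Patient mean above healthy (single-bolus SD) | Share qualifying | Null shift (single-bolus SD) | False improvement per measure | Median |
|---|---|---|---|---|
| 0.5 | 26–60% | 0.02–0.25 | 3.5–15.4% | about 7% |
| 1.0 | 57–88% | 0.01–0.15 | 2.6–7.9% | about 4% |
| 1.5 | 79–98% | 0.00–0.07 | 2.2–3.8% | about 3% |

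Repeat runs put the top of the first row at 15 to 16%. Over means 0.5 to 1.0, false improvement on at least one of the two measures is about 5 to 30%. These shifts are in single-bolus SD and cannot be set beside the participant-level SDs of Step 1.

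**Step 3: frequency of impairment.** For means 0.5 to 1.0, the share impaired on a given measure is 54 to 74% at baseline and 27 to 69% at re-test, with no true effect.

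**Step 4: if ES boluses can also qualify.** The null shift is 0.00 to 0.18 single-bolus SD and false improvement 2 to 10% per measure: weaker, but not removed across the range.

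**Step 5: what the trial could estimate.** Up to 3 boluses per condition give a rough estimate of bolus-to-bolus variance, imprecise with about 12 people. The day-to-day part cannot be estimated, because no one has a second untreated exam. Inter-rater agreement measures neither.

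**The case against.** Four points on the other side have force.

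- **It is called a feasibility study, with blinded rating.** Both are true. The label does not limit the stated objective, which is efficacy. Blinding deals with rater bias, whereas this variation is in the recordings themselves.
- **The effect may be small.** This stands. Candidates are Hoehn and Yahr 2 or 3 with self-reported symptoms, and the background names both measures as key mechanisms in Parkinson disease. If most of those examined qualify, the artefact is close to negligible.
- **The text already sends every VFSS through blinded rating.** This stands, so a reader should not infer that the eligibility reading is reused as the outcome value. What the readable text leaves open is which boluses decide eligibility. Figure 1 is not shown and may say.
- **Repeated boluses carry information.** This also stands: it would be too strong to say that no part of the regression can be estimated.

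Three stronger readings are tempting, but the documents do not support them.

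- *Impairment frequency is 100% at baseline and can only fall.* Statistics lists frequency by parameter, and someone admitted on one measure can become newly impaired on the other. The fall is a tendency.
- *All four primary outcomes are selected on.* PAS and residue are not entry criteria.
- *The immediate ES versus RES contrast is biased too.* That holds only if RES weighs more than ES in eligibility and only eligible people are analysed. In the model it then favours ES by 0.00 to 0.12 single-bolus SD. With equal weight it is unbiased.

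**Conclusion.** The point holds for time-to-LVC and PhAMPC in the pre-post RES comparison. To the extent that RES boluses, or other boluses from the same session sharing its day-to-day variation, contribute to eligibility, both measures and their frequency of impairment are expected to fall without any true effect. The design cannot tell that fall from rehabilitation.

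Confidence is high in the direction and low in the size. Under the Step 2 assumptions with patient means 0.5 to 1.0, the null shift is about 0.01 to 0.25 single-bolus SD and false improvement about 3 to 16% per measure against 2.1% nominal. Where 75% or more qualify it is about 2 to 4%. A reader might infer that any improvement seen would be an artefact. The figures do not show that; they show that the efficacy claim is not supported by this comparison alone. The claim should be reworded; the trial need not be redesigned.

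**What to change.** 1. **Study Objectives and Hypotheses; Statistics.** Restate the long-term efficacy aim as uncontrolled within-participant change in RES at the end of the 4-week program. For time-to-LVC and PhAMPC, report both severity and frequency of impairment as exploratory, not as tests of efficacy. State that the change cannot be separated from regression to the mean because the same exam decides entry. Report how many people had a baseline VFSS and how many qualified, since the size of the artefact depends strongly on that share.
2. **Intervention eligibility.** State whether RES, ES or both decide eligibility, and that the eligibility reading is not reused as an outcome value, in line with the blinded rating already planned.
3. **Only if RES alone, or mainly RES, decides eligibility.** Show baseline ES versus RES in everyone with a baseline VFSS as a sensitivity analysis beside the eligible-only result, where consent covers it. It answers a slightly different question, because it includes symptomatic people without impairment on these measures.

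**Cost.** A more modest claim and a few sentences; no extra exams, visits or patients. Item 3 needs rating of clips already recorded. If the 12 are those treated and 26 to 88% qualify, 12 / 0.881 ≈ 14 to 12 / 0.263 ≈ 46 people would have a baseline VFSS, so about 2 to 34 more people to rate. If the 12 include those withdrawn, no more than 12 are rated in all.
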